**DOCUMENT REVISION HISTORY**

Rev.	Description	Originator	Effective Date
A	Initial Release		6.8.16
B	Revisions based on Investigator review		10.14.16
C	Amendment V 2.0 / 09 Feb 2017		2.14.17
D	Amendment V 3.0 / 30 Mar 2017		3.30.17
E	Amendment V4.0 /		10.18.17

## REVISION HISTORY

Version	Date	Justification for Revision
1.0	18 Aug 2016	Initial version
2.0	09 Feb 2017	

1. Incorporates feedback provided by investigational sites from the Investigator's meeting

2. Provides additional clarity

3. Administrative changes

3.0	30 Mar 2017	Incorporates changes based on FDA feedback
4.0	18 Oct 2017	Add subject contact at the end of each 28-day cycle post the 52 Week visit. Separated out the exit visits from the regular visits to add clarity.

## INVESTIGATIONAL PLAN SUMMARY

Title:	Evaluation of the Effectiveness, Safety and Tolerability of LevoCept (Levonorgestrel-Releasing Intrauterine System) for Long-Acting Reversible Contraception
Protocol #:	CMDOC-0022 Version 4.0 / 18 October 2017
Device Name:	LevoCept Intrauterine Contraceptive; Levonorgestrel-Releasing Intrauterine System (referred to as LevoCept or Study Device throughout this document)
Study Design:	Prospective, multi-center, single-arm, open-label, Phase II clinical study
Study Purpose:	To evaluate the effectiveness, device placement, safety, and tolerability of LevoCept to support commencing a Phase III Clinical Study
Study Duration:	Subject enrollment will take approximately 5 months. Each subject will be followed for 12 months after device placement for the protocol endpoints, and then every 6 months thereafter for up to 24 additional months for those subjects who wish to continue study device use.
Enrollment:	Up to 250 subjects will be consented, screened and have LevoCept placed, with a goal to have 2240 evaluable cycles at 12 months. It is planned that 225 of the 250 subjects will be within the 18-35 year age range, with a total of 2015 evaluable cycles. The remaining 25 subjects will be within the 36-40 year age range.
Investigational Site Information:	This study will be conducted at approximately 16 centers in the U.S.
Follow-up:	
Physical assessment (office visit) will occur at weeks 6, 13, 26 and 52 after placement, with monthly contact. For those subjects who wish to continue study device use after 12 months, follow-up office visits will occur every 6 months with contact at the end of each 28-day cycle beginning after the 52-week visit. Additional visits will be conducted if necessary for safety issues.
 
Follow-up after early study device removal:
 
Subjects requesting LevoCept removal to become pregnant will be followed for either; six (6) months, until they decide to no longer try to conceive or they become pregnant, whichever comes first. All subjects in whom LevoCept is removed, for any reason, will be required to use an alternative contraceptive for the first two weeks following removal. Hormonal contraceptive pills will be reimbursed by the sponsor as a contraceptive option during this

time unless the subject has a MEC category 4 condition precluding their use.

**Study Population:** Pre-menopausal women ages 18–40, at risk for pregnancy, who are interested in using only this intrauterine contraceptive for birth control will be eligible for this study. Subjects must provide written informed consent and meet the study subject selection criteria without any exclusions as outlined in the Clinical Investigation Plan (CIP).

**Primary Effectiveness Outcome:**

The primary outcome measure is effectiveness, evaluated as the absence of pregnancy with failures calculated by the Pearl Index and life-table analysis. All evaluable cycles prior to discontinuation or planned removal will be included in the primary analysis of effectiveness.

**Safety and Other Outcome Measures:**

Safety and other outcome measures include:

Study Device Placement:

- Ease of placement
- Placement success

Safety:

- Serious Adverse Events
- Adverse Events

Tolerability:

- Bleeding and spotting patterns
- Discontinuation rate and reasons for discontinuation

**Subject Selection Criteria**

**INCLUSION CRITERIA**

Subject must meet all of the following criteria to participate in this study:

1. Between 18-40 years of age at the time of study initiation;
  - 1.1 Enrollment will be targeted for 225 subjects aged 18-35 (for safety and effectiveness analyses) and an additional 25 subjects aged 36-40 (for safety only) (note: all subjects will be included in the analysis for device placement and tolerability);
2. Pre-menopausal, as determined by regular menstrual cycle ( $28 \pm 7$  days) for the last 3 months;
  - 2.1 Based on patient history, when not on hormonal contraceptives;
3. Sexually active with a male partner who has not had a vasectomy;
4. Reasonably expected to have coitus at least once monthly during the study period.

5. In a mutually monogamous relationship of at least 3-6 months duration;
6. Seeking to avoid pregnancy for the next 12 months;
7. Willing to use the study device as the sole form of contraception;
8. Willing to accept a risk of pregnancy;
9. Subjects who are age 21 or older, at time of informed consent, must have a normal PAP or ASC-US with negative high risk HPV test result within the appropriate screen timeframe, and prior to LevoCept insertion;
10. Able and willing to comply with all study tests, procedures, assessment tools and follow-up; and
11. Able and willing to provide and document informed consent and Authorization for Release of Protected Health Information (PHI).

### EXCLUSION CRITERIA

A subject will be excluded from participating in the study if **any** of the following conditions apply:

1. Known or suspected pregnancy; or at risk for pregnancy from unprotected intercourse earlier in current cycle;
2. Subject who anticipates separation from her partner for more than 1 cycle within the next 12 months;
3. A previously inserted IUD that has not been removed by the time LevoCept is placed;
4. History of previous IUD complications, such as perforation, expulsion, infection (pelvic inflammatory disease) or pregnancy with IUD in place;
5. Injection of hormonal contraceptive (e.g., Depo-Provera) within the last 10 months;
  - 5.1 Must have had 2 normal menstrual cycles since the last injection;
6. Planned use of any non-contraceptive estrogen, progesterone or testosterone any time during the 12 months of study participation;
7. Postpartum, prior to a minimum of 6 weeks and complete uterine involution;
8. Exclusively breastfeeding before return of menses; Lactating women will be excluded unless they have had two normal menstrual periods prior to enrollment.
  - 8.1 Must have had 2 normal spontaneous menstrual cycles since delivery
9. Unexplained abnormal uterine bleeding (suspicious for serious condition), before evaluation; Immediately post-septic abortion or puerperal sepsis (must wait a minimum of 3 months);
10. Severely heavy or painful menstrual bleeding;
11. Suspected or known cervical, uterine or ovarian cancer, or unresolved clinically significant abnormal pap smear requiring evaluation or treatment.
12. Any history of gestational trophoblastic disease with or without detectable elevated  $\beta$ -hCG levels, or related malignant disease without an intervening normal pregnancy;
13. Any congenital or acquired uterine anomaly that may complicate IUD placement, such as:
  - 13.1 Submucosal uterine leiomyoma

- 13.2 Asherman's syndrome
- 13.3 Pedunculated polyps
- 13.4 Bicornuate uterus
- 13.5 Didelphus or uterine septa
- 14. Any distortions of the uterine cavity (e.g. fibroids), in the opinion of the investigator, likely to cause issues during insertion, retention or removal of the IUD;
- 15. Known anatomical abnormalities of the cervix such as severe cervical stenosis, prior trachelectomy or extensive conization that, in the opinion of the investigator would prevent cervical dilation and study device placement;
- 16. Current or recent (within the last 3 months) untreated acute cervicitis or vaginitis ;
- 17. Known or suspected breast cancer or other progestin-sensitive cancer now or in the past;
- 18. Known acute liver disease or liver tumor;
- 19. Subjects who have an established immunodeficiency;
- 20. High risk for STDs (e.g., multiple sexual partners);
- 21. Known or suspected HIV infection or clinical AIDS;
- 22. Known intolerance or allergy to any component of the LevoCept system; including nickel, silicone or tantalum;
- 23. Subject had LevoCept placed previously or had 2 attempts at placement;
- 24. Known or suspected alcohol or drug abuse within 12 months prior to the screening visit;
- 25. Any general health or behavioral condition that, in the opinion of the Investigator, could represent an increased risk for the subject or would render the subject less likely to provide the needed study information.
- 26. Subject is currently participating or has participated in another clinical study involving another investigational agent within 30 days of the planned LevoCept insertion date or is planning participation in another clinical trial with an investigational agent within 52 weeks (visit 6) after insertion.

### **LevoCept Insertion Timing**

The following must be followed prior to LevoCept insertion to insure adequate contraception coverage:

### **Subjects Using Any Hormonal Birth Control Method**

Subjects using any hormonal birth control method can have LevoCept placed on any day of the menstrual cycle. If the insertion occurs in the first 7 days of the cycle, the hormonal contraception can be discontinued after insertion. If the insertion occurs after the first 7 days of the menstrual cycle, the subject should continue using hormonal contraception for an additional 7 days.

- Subjects using an implant (Implanon/Nexplanon) who have regular cycles, LevoCept should be inserted within seven days of onset of menses and the implant may be removed the same day.

- Subjects using an implant (Implanon/Nexplanon) who have irregular cycles or amenorrhea, LevoCept should be inserted and the implant should be removed seven days after IUD inserted
- Subjects using an implant (Implanon/Nexplanon) with regular cycles but who are beyond seven days of menses, LevoCept may be inserted but removal of implant should occur after seven days.
- Subjects using levonorgestrel IUD can have IUD removed and LevoCept placed on the same day. Insertion can occur on any day of the cycle.

### **Subjects NOT Using Any Hormonal Birth Control Method (includes copper IUDs)**

Subjects NOT using hormonal contraception (including those currently using a copper IUD) must have the IUD inserted in the first 7 days of the menstrual cycle. Removal of a copper IUD and insertion of Levocept may occur on the same day as long as the procedure is performed within the first 7 days of the menstrual cycle.

If pain is present with the subject's current IUD, the subject should not be enrolled.

## **STATISTICAL METHODS**

### **Effectiveness Outcome**

The primary efficacy population will include all subjects aged 18-35 who had a study device successfully placed, provided at least 1 day of e-diary data, and were not pregnant before the IUD was placed.

Effectiveness will be evaluated as the absence of pregnancy during LevoCept use. Pregnancies judged to have occurred during study device use (determined by ultrasound and medical assessments), for which the estimated date of conception was within 7 days after study device removal or calculated date of expulsion, will be included in the per protocol analysis of pregnancies.

The Pearl Index (and 95% confidence intervals) will be calculated for cycles in subjects aged 18-35 at the time of study device placement through the date of LevoCept removal or pregnancy, excluding the following cycles (unless the subject became pregnant in the cycle):

- When back-up contraceptive or emergency contraceptive use was reported by the subject
- When the subject denied having any intercourse.

All pregnancies will be counted in the intent to treat analysis.

Life table analyses will be used as further assessment of pregnancies. Pregnancy rate will also be summarized annually for each of the 3 years and cumulatively.

### **Safety and Other Outcome Measures**

LevoCept ease of placement, placement success, expulsions, and removal success will be descriptively summarized.

Safety evaluations will be based on the incidence of adverse events and serious adverse events and by relationship to the study device or study device placement procedure.

Study device tolerability will be based on changes in bleeding and spotting patterns and study discontinuation (including reasons for discontinuation).

Safety analyses will be based on the experience of all subjects who had attempted study device placement and provided any relevant data. Tolerability analyses will be based on the experience of all subjects who received a study device and provided any relevant data.

Subjects will record frequency and intensity of vaginal bleeding through a daily e-diary. The number of bleeding or spotting days will be summarized for each cycle. In addition, bleeding and spotting will each be summarized separately. Bleeding analyses will include all subjects who had a study device placed and have at least 1 cycle where they were not pregnant and were providing bleeding-related e-diary data on the days in the reference period.

In general, summaries of quantitative variables will include the sample size, mean, median, standard deviation, minimum, and maximum. For qualitative (categorical) variables the summaries will include the number and percentage of subjects in each category.

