## **12.2 Visit 2: LevoCept Placement (Day 1)**

See Section 4.1 for LevoCept insertion timing instructions. Subjects must have a negative urine pregnancy test just prior to LevoCept placement. Initiation of the LevoCept is consistent with standard IUD placement. Refer to the Clinician's Quick Use Guide and Investigator's Brochure for specific instructions.

If placement is unsuccessful, a second attempt may be made on the same day or within one (1) week following the first attempt. If a second attempt is also unsuccessful, the subject will be discontinued early from the study. The need for cervical dilation to facilitate placement of LevoCept will be left to the discretion of the investigator and subject; however, it is recommended that placement be tried first without prior cervical dilation. Use of cervical dilation will be recorded on the case report form. The need for pain control will also be left to the discretion of the investigator and subject. Any medications given for pain control will be recorded on the Concomitant Medications case report form.

Prior to LevoCept placement, the following evaluations will be completed:

- Entry criteria confirmed
- Vital signs and weight
- Pelvic Exam
- Pregnancy test, urine
- Prior and concurrent medications
- Any adverse events.

Following LevoCept placement, the following will be performed:

- LevoCept placement ease
- LevoCept placement pain
- LevoCept position (evaluated by Transvaginal Ultrasound)
- Concomitant contraception
- Need for contraception if LevoCept was not properly placed (If a subject believes the study device may have been expelled or is no longer in place, the subject should call for an urgent study visit and refrain from having sex or use appropriate non-hormonal contraception until further evaluation is completed. (See Section 4.7 for details)

- Review the completed practice diaries and discuss with the subject any further training that is required and answer any questions the subject may have about how to correctly complete the diaries.
- Instruct the subject to contact the site immediately if she thinks she has become pregnant.

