4. Bleeding and spotting

The total number of bleeding or spotting days for each subject at each cycle will be counted. The total number of bleeding and spotting days for each subject at each cycle will also be counted separately.

5. Discontinuation rate and reasons for discontinuation

Removal rates

The removal rate is defined as the percentage of the number of subjects with device removed among the total number of subjects enrolled in the study by that time-point.

Expulsion rates

The expulsion rate is defined as the percentage of the number of subjects with device expulsion among the total number of subjects enrolled in the study by that time-point.

Discontinuation rate

The discontinuation rate is defined as the percentage of the number of subjects discontinued study among the total number of subjects enrolled in the study by that time-point.

Reasons for discontinuation

The following reasons have been collected for exiting study:

- Adverse Event;
- Withdrew Consent;
- Protocol Violation;
- Lost to Follow-up;
- Investigator/Sponsor Decision;
- Pregnancy;
- Screen Failure;
- Other.

5 Analysis Populations

Data analyses will be based on the analysis populations defined below. Analysis populations, including exclusions based on major protocol deviations (PDs), will be reviewed and approved by the Sebelia and its designee. Excluded cases will be documented together with the reason for exclusion.

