5.2 All Enrolled

Enrolled subjects are all screened subjects who underwent the study device placement procedure, regardless of whether the study device was successfully placed or not.

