	16.2.9.2	Vital Signs (All Enrolled Subjects)
	16.2.9.3	Vital Signs – Change from Baseline Results (All Enrolled Subjects)
	16.2.9.4	Physical Examination (All Enrolled Subjects)
	16.2.9.5	Pelvic Examination (All Enrolled Subjects)

13 Appendix 3 Table Layouts

CONFIDENTIAL

Sebela Pharmaceuticals Development LLC
CMDOC-0022

Page x of y

Table 14.1.1
Subject Disposition (All Screened Subjects)

Description	Enrolled [1] (N=xx) n (%)	All Subjects (N=xx) n (%)
Screen Failure		n (%)
Safety Population [2]	n (%)	n (%)
Discontinued 1-Year Study Prematurely	n (%)	n (%)
Completed 1-Year Study	n (%)	n (%)
Entered the Extension Study	n (%)	n (%)
Discontinued Extension Study Prematurely	n (%)	n (%)
Completed Extension Study	n (%)	n (%)
Reason for Discontinuation of 1-Year Study		
Adverse Event	n (%)	n (%)
Withdrew Consent	n (%)	n (%)
Protocol Violation	n (%)	n (%)
Lost to Follow-up	n (%)	n (%)
Investigator/Sponsor Decision	n (%)	n (%)
Pregnancy	n (%)	n (%)
Other	n (%)	n (%)
Screen Failure [3]		n (%)
Reason for Discontinuation of Extension Study		
Adverse Event	n (%)	n (%)
Withdrew Consent	n (%)	n (%)
Protocol Violation	n (%)	n (%)
Lost to Follow-up	n (%)	n (%)
Investigator/Sponsor Decision	n (%)	n (%)
Pregnancy	n (%)	n (%)
Other	n (%)	n (%)

Note: Percentages are based on the number of subjects specified in the column header, i.e. N, unless otherwise specified.

[1] Enrolled subjects are all screened subjects who underwent the study device placement procedure, regardless of whether the study device was successfully placed or not.

[2] Safety population will include all enrolled subjects who underwent a successful study device placement procedure.

[3] Screen failure as primary reason for exiting study collected on the study exit status form.

Reference: Listing xxx.

Program Location: \\xx\xxx\xxx\xxx\xxxxxx\xxxxxxxxxxxxxxxx\xxxx\xxxxx.sas

date

time

CONFIDENTIAL

Sebela Pharmaceuticals Development LLC
CMDOC-0022

Page x of y

Table 14.1.2
Subject Disposition by Site (All Enrolled Subjects)

Description	All Subjects (N=xx) n (%)
Site 1 xxx	
Enrolled	n (%)
Discontinued 1-Year Study Prematurely	n (%)
Completed 1-Year Study	n (%)
Entered the Extension Study	n (%)
Discontinued Extension Study Prematurely	n (%)
Completed Extension Study	n (%)
Site 2 xxx	
Enrolled	n (%)
Discontinued 1-Year Study Prematurely	n (%)
Completed 1-Year Study	n (%)
Entered the Extension Study	n (%)
Discontinued Extension Study Prematurely	n (%)
Completed Extension Study	n (%)

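### The protocol gives two populations for the discontinuation rate, and the SAP reports it only over all enrolled women, so finally failed placements raise a tolerability outcome slightly

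*Protocol*

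**What the plan says.** **Outcome.** The protocol synopsis and section 5.2 both place "Discontinuation rate and reasons for discontinuation" under Tolerability.

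**Population, synopsis.** Under Safety and Other Outcome Measures in the statistical methods, safety analyses use women with an attempted placement. The next sentence sets a different population for tolerability: "Tolerability analyses will be based on the experience of all subjects who received a study device and provided any relevant data".

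**Population, protocol body.** Section 20.7 assigns safety and other outcomes to the ITT/Safety population unless another is noted. Section 20.1 defines that population to include failed placements. Section 20.7 names other populations for bleeding and dyspareunia, but none for discontinuation.

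**SAP.** Section 4.2, item 5: "The discontinuation rate is defined as the percentage of the number of subjects discontinued study among the total number of subjects enrolled in the study". Section 5.2 defines enrolled women as those who underwent the placement procedure, "regardless of whether the study device was successfully placed or not". Section 5.3 narrows the Safety Population to successful placements.

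**Failed placement.** Protocol section 12.2: "If a second attempt is also unsuccessful, the subject will be discontinued early from the study".

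**Output.** Table 14.1.1 (Subject Disposition) has two columns, Enrolled and All Subjects, with the footnote "Note: Percentages are based on the number of subjects specified in the column header, i.e. N, unless otherwise specified". The exit reasons in SAP section 4.2 and Table 14.1.1 include no failed-placement category.

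**The concern.** Discontinuation as a tolerability outcome should describe women who had the device and stopped using it. A woman with no device after her placement attempts is discontinued at the outset and has no experience of use. Counting her mixes an insertion problem with a problem in use. The same event already counts as a failure in the deployment rate of SAP section 4.2, item 1.

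The protocol's Introduction cites early discontinuation of existing intrauterine contraceptives as a motivation for this product, and section 5 says the data are to support starting Phase III. A sponsor reading the rate for that purpose needs insertion failure and discontinuation in use kept apart. The reasons are also affected. With no category of their own, failed placements must be recorded under Other or another general reason, which blurs the second half of the outcome.

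**Working it through.** **Which women are counted**

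| Source | Population for the discontinuation rate | Failed placements in? |
|---|---|---|
| Protocol synopsis | women who received a device | no |
| Protocol 20.1 and 20.7 (default) | all with a placement attempt | yes |
| SAP 4.2 item 5 with 5.2 | all enrolled | yes |
| SAP 5.3 Safety Population | successful placement only | no, but not used for this rate |

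SAP section 8.2 records that the Safety Population was narrowed to successful placements. It does not say which population the discontinuation rate should follow after that change.

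**Inputs.** Planned enrolment is about 250 (protocol section 10). The documents give no placement failure rate and no discontinuation rate, so there is no stated figure to reproduce and both are assumed over a range.

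**Formula.** Let N be enrolled women, F those whose placement finally failed, P = N − F those with a device placed, and D the discontinuations among P. Write f = F/N and d = D/P.

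- SAP rate = (D + F)/N = f + (1 − f)d
- Rate among recipients = D/P = d
- Excess = f + (1 − f)d − d = f(1 − d), which is never negative

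**Results at d = 20% (assumed)**

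| f (assumed) | SAP rate | Excess, points |
|---|---|---|
| 1% | 0.01 + 0.99 × 0.20 = 20.8% | 0.8 |
| 2% | 0.02 + 0.98 × 0.20 = 21.6% | 1.6 |
| 5% | 0.05 + 0.95 × 0.20 = 24.0% | 4.0 |

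**The middle row in counts.** With N = 250 and F = 5, P = 245 and D = 0.20 × 245 = 49. The SAP rate is (49 + 5)/250 = 21.6%, against 49/245 = 20.0%. Of the 54 counted discontinuations, 5 (9.3%) are women who never had a device.

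**Wider range.** For F from 1 to 13 of 250 (0.4% to 5.2%) and d from 10% to 30%, the smallest excess is 0.004 × 0.70 = 0.28 points and the largest is 0.052 × 0.90 = 4.68 points.

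**What is already planned on successful placements only.** Table 14.3.5.3 gives cumulative removal and expulsion rates on the Safety Population, although the SAP section 4.2 text defines both over enrolled women. Tables 14.3.1.5 and 14.3.1.6 give adverse events leading to removal and adverse events as the primary reason for exit, also on the Safety Population. The bleeding summaries use the Safety and ECYC populations. The overall discontinuation rate and its full list of reasons are the tolerability outputs left on all enrolled women.

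**The case against.** The strongest reply is that the SAP follows the protocol body. Sections 20.1 and 20.7 include failed placements by default, and section 20.2 requires disposition on all enrolled women. One synopsis sentence points the other way. This stands: a reader might infer that the SAP departs from a clear protocol rule, but the root is a contradiction inside the protocol.

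Inclusion criterion 1.1 also says that all subjects enter the tolerability analysis. That note sits in the item on the two age bands and most naturally brings the 36–40 group in. It does not address failed placements, but the text does not rule out the broader reading.

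A reader might infer that every failed insertion counts against the device. It does not: section 12.2 allows a second attempt, and success there is not a discontinuation. A reader might also infer that these women are reported as intolerant of the device. They are not, since exit reasons are tabulated separately. They are only included in a rate that carries the tolerability label.

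Finally, planned outputs allow a partial separation. Table 14.1.1 prints the Safety Population count, Table 14.3.5.1 counts women with no deployment at either attempt, and Listing 16.2.1.2 gives days on device and exit reason for each woman. If every failed placement is recorded as discontinued, the overall recipient rate can be back-calculated. The reasons cannot be recovered from the tables.

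The effect is also small for a descriptive single-arm study with no threshold on this rate. At d = 20% and N = 250 the 95% half-width is 1.96 × √(0.20 × 0.80/250) ≈ 5 points, and the shift can only count against the device.

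**Conclusion.** The concern holds as a minor point. The protocol gives two incompatible populations for the discontinuation rate. The SAP adopts the one that includes failed placements without recording the choice, and no planned table gives the rate or its reasons among device recipients.

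As a measure of tolerability in use, the planned rate is shifted upward by f(1 − d): about 0.8 to 4.0 points for f = 1% to 5% at d = 20%. Both inputs are assumptions. The upper figure needs a 5% final failure rate, for which the documents offer no support. The planning average of 10 evaluable cycles per woman does not supply d, because it is a figure for evaluable cycles and not a retention forecast. The direction of the shift is certain and follows from the definitions; its size is not. As a disposition figure, the all-enrolled rate is correct and should stay.

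**What to change.** 1. In SAP section 4.2, item 5, define the tolerability discontinuation rate and its reasons on the Safety Population (successful placement). This matches the denominator Table 14.3.5.3 already uses.
2. Add a Safety Population column to Table 14.1.1 for that rate and its reasons. Keep the Enrolled column as disposition.
3. Show final placement failure as its own line in Table 14.1.1, derived from the placement data behind Table 14.3.5.1, so that it is not absorbed into Other.
4. Reconcile the protocol synopsis sentence with section 20.7, and record the chosen population in SAP section 8.2. In the same edit, align the section 4.2 text for removal and expulsion rates with Table 14.3.5.3.

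The cost is one table column, one table line and a few sentences. No new data are needed.
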